1 SUMMARY

Full title	Donor derived cell-free DNA and rejection of kidney allografts
Coordinating Investigator	Pr [name]
Scientific Director (if applicable)	[name]
Sponsor	Organ X Foundation
Scientific justification	
Allograft rejection is a major problem worldwide and results in the loss of thousands of transplants every year, with devastating consequences for patients in terms of mortality, morbidity and quality of life. With a prevalence of approximately 20% in the first-year after kidney transplantation, allograft rejection also represents a considerable economic burden for health care systems with the associated downstream cost related to graft failure and return to dialysis. The standard strategy to monitor rejection is based on surveillance of nonspecific functional markers such as serum creatinine level, estimated glomerular filtration rate, proteinuria and circulating donor-specific anti-HLA antibodies (DSA), which lack sensitivity and specificity. The current gold standard for diagnosing allograft rejection is the biopsy which is a potentially harmful, costly and often unnecessary procedure.
 
Recently, one promising non-invasive biomarkers has emerged in various fields such as oncology or gynecology for the monitoring of the patients: the cell-free DNA. In transplantation, donor-derived cell-free DNA (dd-cfDNA) detected in the blood of transplant recipients has been proposed as a noninvasive biomarker for the detection of rejection. However, dd-cfDNA has not been assessed in an unselected and deeply phenotyped population, with the comparison to the conventional parameters including functional, clinical or immunological factors to monitor patients and detect rejection.

Main objective and primary endpoint	
Main objectives
 
To assess the association of dd-cfDNA with the presence, activity and severity of allograft rejection, and determine whether dd-cfDNA adds value to standard of care monitoring parameters in detecting kidney allograft rejection

	
Primary endpoint Kidney allograft rejection (all causes) Time Frame: Up to 10 years after kidney transplantation

Design of the study	
Type of study: Multicenter international study Time Perspective: prospective

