Population of study participants	
Derivation cohort: Prospective cohort of kidney transplant recipients recruited in 2 French centers
 
Validation cohort: kidney transplant recipients in 11 North-American centers and 1 Belgian center with clinical, biological, histological and immunological data, and dd-cfDNA assessment.

Inclusion criteria	
 Recipients transplanted from a deceased or living donor, who undergone a kidney allograft biopsy with clinical, biological, histological and immunological data. Written informed consent at the time of transplantation for the center database.
Exclusion criteria	
 Combined organ transplantation Pregnant women Bone marrow transplant
Interventions or product under investigation	
This study involves minimal risk and constraints. The intervention consists in the evaluation of the risk of allograft rejection based on parameters measured as part of the standard of care and dd-cfDNA. No medicinal product is under investigation in this protocol.

Other interventions added by the study	
Gene expression measurement in allograft biopsies

Expected benefits for the participants and for society	
There will be no immediate individual benefit for the patient to participate in the study.
 
This study will be the first that evaluates the independent association of dd-cfDNA with rejection and its added value in addition to conventional features to predict kidney allograft rejection.
 
This first integrative system will improve the patient monitoring and will help physicians in decision-making process.

Minimal risks and constraints added by the study	
The intervention added by the study represents minimal risk and constraints for the patient as it will be embedded within the standard of care.
 
No additional puncture is performed; only one additional blood tube is taken for the measurement of dd-cfDNA.

Scope of the study	Kidney transplantation; non-invasive diagnosis of rejection for improving patient monitoring
Anticipated number of participants	
Number of participants with post-transplant risk evaluation:
 
Derivation prospective cohort: 1000 patients
 
External validation cohort: 1500 patients

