
Statistical analysis
	
Continuous variables will be described using means and standard deviations (SDs) or median and the interquartile range. We will compare means and proportions between groups using Student's t-test, analysis of variance (ANOVA) (Mann-Whitney test for donor specific antibodies (DSA) mean fluorescent intensity) or the chi-square test (or Fisher's exact test if appropriate).
 
We will evaluate the association between the dd-cfDNA levels and each allograft diagnosis (ABMR, TCMR, Mixed rejection, glomerulitis without rejection, polyomavirus nephritis, fibrosis, borderline changes, no specific lesions). Then, to investigate the association of dd-cfDNA with rejection severity, we will compare the mean dd-cfDNA level according to each active and chronic Banff lesion score (ranked from 0 to 3).
 
Evaluation of the association between dd-cfDNA and rejection
 
The associations between allograft rejection and clinical, functional, and immunologic factors will be first computed using logistic regression analyses. The factors identified in these analyses will be thereafter included in a final multivariable analysis if the p-value of the Wald test is < 0.1. Multivariable logistic regression analysis will be performed using a stepwise backward elimination until each predictor is associated with allograft rejection with a p-value below 0.05. The internal validity of the final model will be confirmed using a bootstrap procedure, which involves generating 1,000 datasets derived from resampling the original dataset and permitting the estimation of the biased corrected 95% CI and the accelerated bootstrap OR.
 
Assessment of the added value of dd-cfDNA
 
To evaluate the added value of dd-cfDNA, we will assess the performances of the reference model (including independent standard of care predictors of the final multivariable model) with and without dd-cfDNA to evaluate to risk of rejection. The performances of the models to predict rejection will be evaluated with the use of the accuracy of the model, which will be assessed based on its discrimination ability and calibration performance. For each model, the discrimination ability (i.e., the ability to separate patients with different prognoses) of the final model will be evaluated using Area under the curve (AUC). Calibration (the ability to provide unbiased rejection predictions in groups of similar patients) will be assessed based on a visual examination of the calibration plots.

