
	
We will follow the TRIPOD (Transparent Reporting of a Multivariable Prediction Model for Individual Prognosis or Diagnosis) statement for reporting multivariable prediction model development and validation.
 
Sensitivity analyses: We will investigate the independent association of dd-cfDNA with rejection and its added value in predicting rejection in different clinical scenarios (biopsies performed during the first year or after one-year post-transplantation, according to the subtypes of rejection, protocol biopsies or biopsies performed for clinical indication) and according to the patient ethnicity.
 
We will use R (version 4.1.2, R Foundation for Statistical Computing) and STATA (v17) for the descriptive and prediction analyses. Values of $p < 0.05$ will be considered significant, and all tests will be 2-tailed.

Sources of monetary support	The study is funded by the OrganX Foundation

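### Severity is assessed by comparing mean dd-cfDNA across Banff grades 0-3 with no test that uses the ranking, so a significant result would not by itself show that dd-cfDNA rises with grade.

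*Combined protocol and SAP*

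**What the plan says.** Section 1 Summary, Main objective and primary endpoint, sets the aim: "To assess the association of dd-cfDNA with the presence, activity and severity of allograft rejection". Severity therefore belongs to the main objective.

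The Statistical analysis entry of the same section gives severity one analysis: "we will compare the mean dd-cfDNA level according to each active and chronic Banff lesion score (ranked from 0 to 3"). The wording recognises that the grades are ordered, but no test is named there.

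The test has to come from the general rule at the start of that entry: "We will compare means and proportions between groups using Student's t-test, analysis of variance (ANOVA"). The one stated exception is the "Mann-Whitney test for donor specific antibodies (DSA) mean fluorescent intensity", which does not concern dd-cfDNA. With four grades, ANOVA is the only listed test of means that applies.

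The plan contains no trend test, linear contrast, ordinal model, rank correlation or per-grade slope. The logistic models take rejection (yes or no) as the outcome, so they do not address lesion grade.

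**The concern.** A severity claim is a claim about direction: the higher the lesion grade, the higher the dd-cfDNA. A one-way ANOVA on four grades asks whether any of the four means differ. It gives the same p-value if the grade labels are shuffled.

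This has two consequences:

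- **Interpretation (the main one).** A significant F test can come from a pattern with no severity gradient, such as a raised grade 1 with grades 2 and 3 back at the level of grade 0.
- **Power.** If the true rise is close to linear, two of the three degrees of freedom are spent on departures from the line, and power is lost against a 1-df test.

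The plan also specifies no estimate of the change in dd-cfDNA per grade with a confidence interval, which is what a reader would need to judge how strongly the marker tracks severity.

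**Working it through.** The plan gives no power, SD, slope or grade shares for this analysis, so there is no figure of its own to reproduce.

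**Inputs from the plan.** "Derivation prospective cohort: 1000 patients" (N = 1,000); 1,500 patients for validation; "Values of $p < 0.05$ will be considered significant"; "all tests will be 2-tailed"; four grades.

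**Assumptions.** Grade shares of 70/14/10/6% over grades 0-3, with 85/8/5/2% as a sparser alternative; effects in SD units; one independent biopsy per patient; common SD.

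**Formulas.** With n_g = N × share, mean μ_g at grade g (SD units) and overall mean μ̄:

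- ANOVA noncentrality: λ_F = Σ n_g(μ_g − μ̄)², referred to F with 3 and N−4 df.
- Trend noncentrality: λ_T = S_xy²/S_xx, with S_xx = Σ n_g(g − ḡ)² and S_xy = Σ n_g(g − ḡ)μ_g, referred to F with 1 and N−4 df.

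For 70/14/10/6%, ḡ = 0.14 + 0.20 + 0.18 = 0.52 and S_xx = 1000 × (0.14 + 0.40 + 0.54 − 0.52²) = 809.6.

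**1. A significant F test without a gradient.** Means 0/0.3/0/0:

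- μ̄ = 0.14 × 0.3 = 0.042, so λ_F = 1000 × (0.14 × 0.09 − 0.042²) = 10.84 and ANOVA power is 80%.
- S_xy = 140 × 0.48 × 0.3 = 20.16, so λ_T = 20.16²/809.6 = 0.50 and trend power is 11%.

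With shares 85/8/5/2% the same pattern gives 56% and 15%.

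**2. Power for a linear rise, in general.** Here λ_F = λ_T. By the large-sample chi-square approximation, λ = (1.96 + 0.842)² = 7.85 gives 80% at 1 df and 64.5% at 3 df. Reaching 80% at 3 df needs λ = 10.90, and 10.90/7.85 = 1.39. This is a relative efficiency under exact linearity.

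**3. Power for a linear rise, N = 1,000.** λ = b² × 809.6 for slope b, or b² × 402.4 for the sparser shares:

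| Slope per grade | λ (70/14/10/6) | ANOVA / trend | λ (85/8/5/2) | ANOVA / trend |
|---|---|---|---|---|
| 0.10 SD | 8.10 | 66% / 81% | 4.02 | 36% / 52% |
| 0.15 SD | 18.22 | 96% / 99% | 9.05 | 71% / 85% |
| 0.20 SD | 32.38 | 99.9% / about 100% | 16.10 | 93% / 98% |

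At N = 1,500 with shares 70/14/10/6%, 0.10 SD gives 84% / 94%.

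**4. Limits of a trend test** (N = 1,000, shares 70/14/10/6%):

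| Means, grades 0-3 (SD) | λ_F | λ_T | ANOVA | Trend |
|---|---|---|---|---|
| 0 / 0 / 0 / 0.4 | 9.02 | 4.38 | 71% | 55% |
| 0 / 0.3 / 0.3 / 0.3 | 18.90 | 14.73 | 97% | 97% |
| 0 / 0.3 / 0.3 / 0 | 16.42 | 5.15 | 94% | 62% |
| 0 / 0.4 / 0.3 / 0.1 | 23.54 | 9.17 | 99% | 86% |

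The first two rows are monotone but not linear, and the trend test has no advantage there. In the last two, dd-cfDNA falls at the higher grades, yet the trend test is often significant.

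**5. Skewness.** A simulation with lognormal data (log-SD 1, shares 70/15/10/5%, N = 1,000, 4,000 runs, log-slope 0.1 per grade) found significance in 48% by ANOVA on raw values, 61% by Kruskal-Wallis, 73% by Spearman and 79% by linear regression of log dd-cfDNA on grade. With a 0.3 log-scale shift in grade 1 only, Spearman was significant in 38% and the log-scale linear trend in 13%. A rank-based trend is therefore not full protection either.

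**The case against.** The other side has four fair arguments.

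- **ANOVA is inferred.** The severity sentence names no test. This stands as a matter of wording: the defect is an unnamed test whose default is ANOVA. If the sponsor intends something else, the plan still has to say so.
- **The power loss depends on the scenario.** This stands. A reader might infer that the severity analysis is under-powered. The documents do not support that: they give no effect size, SD or grade shares, and with 70/14/10/6% both tests exceed 99% power at 0.2 SD per grade. For a rise at grade 3 only, ANOVA does better. The 39% figure compares two tests under exact linearity and says nothing about whether this study is large enough.
- **A significant trend does not prove a monotone rise.** This stands too. A reader might conclude that severity should be claimed on the trend test alone, but the last two rows of step 4 show why that rule would be unsound.
- **The means at each grade would expose an odd pattern.** This stands in part. A grade-1-only shift would be visible in the four means, and the plan nowhere says that an omnibus p-value alone establishes severity. But it gives no rule for reading the means and no intervals around them.

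The multivariable rejection model and the added-value comparison do not use this test and are unaffected.

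**Conclusion.** The concern holds, mainly as one of interpretation. The severity component of the main objective has no named test, and the test that the general rule implies ignores the order of the grades. A significant result would not show that dd-cfDNA rises with grade: a grade-1-only shift of 0.3 SD would be declared significant in 80% of studies by ANOVA and 11% by linear trend (56% and 15% with sparser high grades).

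The power loss is secondary and conditional on a roughly linear rise. It matters for small slopes or sparse high grades and largely disappears by 0.2 SD per grade. All effect sizes and grade shares are assumptions, and each biopsy is treated as independent. The change is worth making because it is cheap and bears on a stated objective; it does not put the other analyses in doubt.

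**What to change.** In section 1 Summary, Statistical analysis, complete the severity sentence so that, for each Banff lesion, the plan:

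1. names a 1-df trend test as the primary severity test: Jonckheere-Terpstra, or regression of dd-cfDNA (log-transformed if skewed) on the 0-3 grade;
2. reports the change in dd-cfDNA per grade with its 95% CI;
3. reports the mean or median at each grade with its CI, and a secondary test of departure from trend;
4. claims an association with severity only when the trend is significant and the per-grade estimates are consistent with a monotone rise.

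The cost is a few lines of text, with no new data, patients or procedures. The downside is lower power for non-monotone patterns and for some monotone ones, such as a 0.4 SD rise at grade 3 only (trend 55%, ANOVA 71%). The secondary test and the per-grade estimates are kept to bring such patterns to light.

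### The standard-of-care reference model is chosen by p-value, so named monitoring markers can drop out and dd-cfDNA can be credited with their information

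*Combined protocol and SAP*

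**What the plan says.** In the combined protocol and SAP, section 1, the row *Main objective and primary endpoint* sets out to "determine whether dd-cfDNA adds value to standard of care monitoring parameters in detecting kidney allograft rejection". The row *Scientific justification* gives serum creatinine, eGFR, proteinuria and circulating DSA as the markers in current use. They are offered as examples, not as a closed list.

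In the row *Statistical analysis*, under *Evaluation of the association between dd-cfDNA and rejection*, the first step is: "The associations between allograft rejection and clinical, functional, and immunologic factors will be first computed using logistic regression analyses". A factor is then "included in a final multivariable analysis if the p-value of the Wald test is < 0.1", and that model is reduced "using a stepwise backward elimination until each predictor is associated with allograft rejection with a p-value below 0.05". Under *Assessment of the added value of dd-cfDNA*, the comparison rests on the "reference model (including independent standard of care predictors of the final multivariable model) with and without dd-cfDNA".

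The text gives no list of candidate factors, forces no marker into the model, and does not say whether dd-cfDNA is in the model while other predictors are being eliminated. The sensitivity analyses cover time since transplantation, rejection subtype, biopsy indication and ethnicity. None uses a full standard-of-care model.

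**The concern.** The objective names one comparator and the analysis uses another. The first is the monitoring that clinicians already have. The second is whatever part of it reaches significance in this sample. A useful marker can be removed because its p-value fell on the wrong side of 0.05. If it is correlated with dd-cfDNA, dd-cfDNA then picks up part of what it carried.

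Both halves of the main objective depend on this model. The adjusted odds ratio of dd-cfDNA may be tested with relevant covariates missing, and the AUC gain may be measured against a weakened comparator. The risk is greater if dd-cfDNA is itself in the model during elimination. Correlated markers can then be removed because dd-cfDNA is present, and they are missing when dd-cfDNA is taken out to form the reference model.

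**Working it through.** The plan gives no AUC, effect size or precision calculation, so there is no stated figure to reproduce.

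**Inputs from the documents.** Derivation cohort of 1000; entry at Wald p < 0.1; elimination to p < 0.05; two-sided tests.

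**Assumptions.** One record per patient. An event rate of 20%, borrowed from the first-year prevalence in *Scientific justification*, with 10% and 30% also run. All odds ratios (ORs) and correlations are assumed.

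**Step 1: chance that a real marker fails p < 0.05.** For a marker in SD units, SE(log OR) ≈ √[VIF / (N·p·(1−p))], where VIF is the variance inflation from correlated covariates. With N = 1000, p = 0.2 and VIF = 1, SE = 1/√160 = 0.079. Then P(dropped) = Φ(1.96 − z) − Φ(−1.96 − z), with z = ln(OR)/SE. For OR 1.2, z = 0.182/0.079 = 2.31 and P = 0.365.

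| Events | VIF | OR 1.1 | OR 1.2 | OR 1.3 | OR 1.5 |
|---|---|---|---|---|---|
| 10% | 1 | 85% | 59% | 30% | 3% |
| 20% | 1 | 77% | 37% | 9% | 0.1% |
| 30% | 1 | 72% | 25% | 3% | 0.0% |
| 20% | 2 | 86% | 63% | 35% | 5% |

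**Step 2: AUC gain from dd-cfDNA.** 300 to 500 derivation sets of 1000 were simulated, with four real standard markers, six noise candidates and dd-cfDNA. AUC was taken in a large simulated external sample. *Fixed* keeps all four real markers. *Out* applies the planned rule among standard factors only. *In* applies it with dd-cfDNA in the model. Correlations are given as marker–marker / marker–dd-cfDNA.

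| Marker ORs per SD | dd-cfDNA OR | Correlations | Events | Fixed | Out | In | Any real marker lost: Out / In |
|---|---|---|---|---|---|---|---|
| 1.6, 1.3, 1.3, 1.2 | 2.0 | 0.2 / 0.2 | 20% | 0.045 | 0.047 | 0.051 | 25% / 68% |
| same | 2.0 | 0.4 / 0.4 | 20% | 0.030 | 0.032 | 0.037 | 28% / 86% |
| 1.2 (all four) | 2.0 | 0.3 / 0.4 | 20% | 0.039 | 0.042 | 0.063 | 29% / 97% |
| 1.8, 1.6, 1.5, 1.4 | 2.0 | 0.2 / 0.3 | 20% | 0.023 | 0.023 | 0.024 | 0% / 10% |
| 1.6, 1.3, 1.3, 1.2 | 2.0 | 0.3 / 0.4 | 10% | 0.031 | 0.035 | 0.048 | 48% / 96% |
| same | 2.0 | 0.3 / 0.4 | 30% | 0.027 | 0.027 | 0.033 | 6% / 64% |
| 1.5, 1.2, 1.2, 1.1 | 3.0 | 0.2 / 0.5 | 20% | 0.032 | 0.032 | 0.081 | 1% / 97% |
| 1.6, 1.3, 1.3, 1.2 | 1.0 | 0.2 / 0.4 | 20% | −0.001 | −0.001 | 0.000 | 62% / 69% |

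Mean overstatement is 0.000 to 0.004 for *Out* and 0.001 to 0.049 for *In*. Further runs with other assumed inputs extended these to 0.006 and 0.061. With no effect of its own (last row), dd-cfDNA shows essentially no gain under any rule.

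**Step 3: false independent association.** dd-cfDNA has no effect of its own and stays out of the selection. Its adjusted test is at 0.05, with 1000 records and 20% events.

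- Six mutually independent markers (OR 1.6, 1.25, 1.2, 1.15, 1.15, 1.1), each correlated r with dd-cfDNA: false positives were 6–10%, 14–15% and 21–25% across repeated runs at r = 0.20, 0.30 and 0.35. With all six retained the rate was about 4.5–6.5%. In this structure the markers explain 6r² of the variance of dd-cfDNA: 6 × 0.04 = 24%, 6 × 0.09 = 54% and 6 × 0.1225 = 73.5%.
- The same markers correlated 0.3 with each other: about 5–7%. They now explain 6r²/(1 + 5 × 0.3) = 6r²/2.5, that is 9.6%, 21.6% and 29.4%.
- Four stronger independent markers (OR 1.6, 1.5, 1.4, 1.3, or 2.0, 1.6, 1.5, 1.4): about 2–6%, no material inflation.

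**The case against.** The strongest reply is that strong markers survive. With about 200 events, a marker with OR 1.5 per SD and little collinearity is lost about once in a thousand samples. Four markers at OR 1.6, 1.5, 1.4 and 1.3 were all kept in about 85% of simulated trials. The documents give no odds ratio, so weak markers cannot be presumed. Losing one of creatinine and eGFR costs little, since they are near duplicates. The endpoint runs up to 10 years in biopsied patients, so events may exceed 20%, which would reduce the losses. If dd-cfDNA is kept out of the selection, the AUC overstatement is at most about 0.006. All of this stands, and it limits the size of the problem.

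It does not remove the mismatch with the objective. The bootstrap is described for the interval and odds ratio of the final model, and resampling cannot restore an omitted marker. External validation does not help if the same reduced reference model is carried over. TRIPOD governs reporting, not the choice of comparator.

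A reader might infer that markers will be dropped, that the false-positive rate necessarily exceeds 5%, or that dd-cfDNA could gain AUC from nothing. The documents support none of these: the first two depend on unstated marker strengths and correlations, and the simulations did not show the third. Nor can the larger AUC figures be taken as the plan's behaviour. The subsection heading and the definition of the reference model suggest that dd-cfDNA is present during elimination, but the text does not say so.

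**Conclusion.** The concern holds as a risk. The reference model is data-driven, nothing guarantees that it contains the monitoring named in the summary, and any resulting bias tends to favour dd-cfDNA.

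With dd-cfDNA out of the selection, the effect on AUC is small (about 0.000 to 0.006). The effect on the independent association runs from no inflation, with correlated or strong markers, to about 20–25%, with many weak, mutually independent markers that together explain most of dd-cfDNA. With dd-cfDNA in the elimination model, the AUC gain can be overstated by up to about 0.05 to 0.06. In the worst tabulated case it rises from 0.032 to 0.081.

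These figures rest on 1000 records, mainly 20% events, and assumed odds ratios and correlations. The point should be fixed because the remedy is cheap and the main comparison depends on it. The documents do not show that the planned result would be invalid.

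**What to change.** Before analysis, write down a fixed reference model: creatinine or eGFR (one of the two), proteinuria, DSA, and a short list of clinical factors such as time since transplantation and biopsy indication. Keep every term whatever its p-value, and state that dd-cfDNA plays no part in choosing the list. Take both the adjusted odds ratio of dd-cfDNA and the comparison with and without it from this model, in the derivation and the validation cohorts. Keep the stepwise model as a sensitivity analysis, with the selection repeated inside each bootstrap dataset.

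This changes SAP wording only. The inclusion criteria already require clinical, biological and immunological data. A few weak predictors will use a few degrees of freedom, which about 200 events (20% of 1000, assumed) can support. The reported gain may be slightly smaller.

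### The bootstrap said to confirm the model's internal validity yields only an odds ratio and a confidence interval; no optimism correction of AUC or calibration is specified

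*Combined protocol and SAP*

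**What the plan says.** All of this is in section 1 Summary.

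- **Selection** (Statistical analysis, part on the association between dd-cfDNA and rejection). Factors with a univariable Wald p-value below 0.1 enter a multivariable logistic model, which is reduced by "stepwise backward elimination until each predictor is associated with allograft rejection with a p-value below 0.05".
- **Bootstrap** (same part). "The internal validity of the final model will be confirmed using a bootstrap procedure, which involves generating 1,000 datasets", the stated result being "permitting the estimation of the biased corrected 95% CI and the accelerated bootstrap OR". No other output is named, and the text does not say whether the screen and the elimination are repeated in each resample.
- **Performance** (next part, on added value). The models compared are "the reference model (including independent standard of care predictors of the final multivariable model) with and without dd-cfDNA". Discrimination of the final model is measured by AUC, and calibration "will be assessed based on a visual examination of the calibration plots". Neither optimism nor shrinkage is mentioned, and the cohort in which the plots are drawn is not stated.
- **Size** (anticipated number of participants). "Derivation prospective cohort: 1000 patients" and "External validation cohort: 1500 patients".
- **Reporting.** TRIPOD is to be followed for reporting model development and validation.

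**The concern.** When the same data are used to choose predictors, estimate coefficients and measure performance, AUC comes out too high and predicted risks too extreme. Internal validation of a prediction model has to measure that optimism. A bias-corrected interval and a bootstrap odds ratio address a different question, the uncertainty of the coefficients. The bias correction in that sentence belongs to the interval, not to the performance of the model.

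The plan therefore claims confirmed internal validity on outputs that cannot show it, and then reports AUC and calibration from the predictors of that same model. The summary expects the resulting system to help physicians make decisions, so the absolute AUC and the predicted risks matter, and not only the comparison with and without dd-cfDNA.

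**Working it through.** The documents state no figure for this point, so there is none to reproduce. The check has a logical part and a simulation that shows the likely size.

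**1. A calibration plot in the fitting data cannot reveal overfitting.** Maximum likelihood for an unpenalised logistic model sets Σ(y − p) = 0 and Σ(y − p)xⱼ = 0 for each predictor. Hence Σ(y − p)·LP = 0 for the linear predictor LP. Regressing y on LP in the same data therefore returns intercept 0 and slope 1. In every simulated setting the in-sample slope was 1.000.

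**2. Inputs.** From the plan: n = 1000 for derivation, the p<0.1 screen, and elimination to p<0.05. Assumed, because the documents do not give them:
- 10, 20 or 40 candidate standard-of-care factors, of which five have a true effect and the rest are independent noise;
- 10%, 20% or 30% events (the summary's 20% is a first-year background prevalence; 1000 × 0.20 = 200 events);
- true AUC with dd-cfDNA of 0.73, 0.81 or 0.88;
- log-odds ratios per SD in the ratio 0.70 (dd-cfDNA) : 0.15 : 0.20 : 0.30 : 0.45 : 0.60, pairwise correlation 0.2;
- dd-cfDNA always kept in the full model, and removed with a refit for the reference model.

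This gives 27 settings, with 300 replicates each. True performance was taken in 20,000 new patients.

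**3. Quantities.** True optimism = AUC in the fitting data − AUC of the same model in new patients. Bootstrap optimism = mean over resamples of [AUC of the resample's model in the resample − AUC of that model in the original data]. This was computed once with the selected variables held fixed and once with the selection repeated.

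**4. Results at 20% events, model with dd-cfDNA.**

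| True AUC | Candidates | True optimism | Fixed-model bootstrap (share found) | Selection-repeating bootstrap | Slope in new patients |
|---|---|---|---|---|---|
| 0.73 | 10 | 0.0121 | 0.0063 (52%) | 0.0138 | 0.94 |
| 0.73 | 20 | 0.0176 | 0.0064 (36%) | 0.0222 | 0.90 |
| 0.73 | 40 | 0.0282 | 0.0096 (34%) | 0.0390 | 0.87 |
| 0.81 | 10 | 0.0089 | 0.0047 (53%) | 0.0093 | 0.96 |
| 0.81 | 20 | 0.0121 | 0.0056 (46%) | 0.0151 | 0.94 |
| 0.81 | 40 | 0.0171 | 0.0068 (40%) | 0.0253 | 0.92 |
| 0.88 | 10 | 0.0058 | 0.0041 (71%) | 0.0066 | 0.96 |
| 0.88 | 20 | 0.0073 | 0.0039 (53%) | 0.0095 | 0.96 |
| 0.88 | 40 | 0.0107 | 0.0041 (38%) | 0.0158 | 0.93 |

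Over all 27 settings, optimism is 0.005 to 0.043 (reference model 0.005 to 0.049) and the new-data slope 0.80 to 0.98 (reference model 0.76 to 0.97). The worst case is 10% events, AUC 0.73 and 40 candidates. Standard errors are at most 0.0015 for optimism (reference model 0.0017) and 0.008 for slope.

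**5. What the slope means for a predicted risk.** For a predicted 60%, pivoting at a mean risk of 20%: logit(0.20) + slope × [logit(0.60) − logit(0.20)] = −1.386 + slope × 1.792. Slope 0.87 gives 0.173, a risk of 54.3%. Slope 0.96 gives 0.334, a risk of 58.3%.

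**6. Added value of dd-cfDNA.** The apparent AUC gain was 0.0005 to 0.006 below the new-data gain in every setting (for example 0.037 against 0.038), so it is not inflated.

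**7. Precision of the external cohort** (1500 patients, 20% events, AUC 0.73/0.81/0.88; 1.96 × empirical SD over 400 simulated cohorts, one frozen model from 20 candidates). Half-widths are 0.032/0.027/0.022 for AUC, 0.16/0.14/0.12 for slope and 0.018/0.017/0.015 for the paired AUC difference.

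**8. Second simulation, different assumptions** (15, 30 or 50 independent candidates; six true predictors with log-odds ratios from 0.7 to 0.15 per SD; 200 replicates). At 20% events, optimism is 0.018/0.023/0.025 and slope 0.92/0.88/0.88. At 10% events, optimism is 0.022/0.036/0.049 and slope 0.89/0.85/0.78. Direction and order of size agree.

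**The case against.** The best defence is that the bootstrap sentence stands under the association heading, where an odds ratio with an interval is a coherent output. On that view the only fault is too broad a label. The main objective is association and added value, and the AUC gain is not inflated; any error there is conservative. Overfitting is met by design through 1500 patients at other centres and the commitment to TRIPOD. The size rests wholly on assumptions, and the larger values need 40 candidates, mostly noise, or 10% events. With 10 to 20 candidates and 20% events, optimism is only 0.006 to 0.018 and is below the sampling error of the external AUC. Repeating the selection also over-corrects, for example 0.0253 against a true 0.0171. Finally, the text is a summary and does not exclude an optimism correction.

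Most of this stands as a limit on severity. It does not remove the point. The sentence claims internal validity of the model whose predictors feed the performance analysis, and nothing there measures overfitting. The statistical text does not say that the frozen model will be applied to the external cohort or which measures will be computed there, and a reporting guideline does not specify an analysis. Optimism below the sampling error is still a bias in one known direction. Despite its over-correction, the selection-repeating bootstrap was closer to the truth than the fixed-model one for AUC in 26 of 27 settings and for slope in 23 of 27.

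**Conclusion.** The concern holds. Followed as written, the plan reports apparent derivation AUC and calibration for a data-selected model while stating that its internal validity is confirmed. Under the assumptions above, at about 200 events, the AUC of the model with dd-cfDNA is overstated by 0.006 to 0.028, and a predicted risk of 60% corresponds to about 54% to 58%. The error grows with fewer events or more candidates. The conclusion on added value is little affected, and the external cohort reduces the consequence without making the claim true. Severity is minor to moderate. The direction is secure; the size depends on the assumed number of candidates, event rate and true AUC.

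**What to change.** Replace the bootstrap sentence with wording such as:

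> In each of 1,000 resamples the Wald p<0.1 screen and the backward elimination of the standard-of-care factors will be repeated, with dd-cfDNA kept in the full model and removed for the reference model. Each resulting model will be evaluated in the resample and in the original data, and optimism-corrected AUC, AUC difference and calibration slope will be reported. Separately, bias-corrected and accelerated 95% CIs for the ORs will be obtained by refitting the fixed final model in the resamples.

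The separate refit is needed because a covariate of the final model is dropped in 7% to 25% of selection-repeating resamples. The wording makes explicit that dd-cfDNA is always in the full model, which the plan only implies.

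Secondary addition to the calibration sentence:

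> The derivation models with and without dd-cfDNA will be applied unchanged to the external validation cohort; calibration intercept and slope with 95% CIs will be reported next to the calibration plot, with AUC and paired AUC difference.

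The cost is wording and computing, with no extra patients or data. Derivation AUCs will look slightly less favourable. Over-correction of AUC is at most 0.002, 0.006 and 0.014 with 10, 20 and 40 candidates, so a short pre-specified candidate list helps.
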